7.1 Toxicity and Adverse Events

All the adverse events will be coded using the Medical Dictionary for Regulatory Activities (MedDRA).

The toxicity evaluation will be coded with the National Cancer Institute Common Terminology Criteria for Adverse Events (NCI-CTCAE) v4.

Treatment-emergent adverse events (TEAE) are defined as any adverse events aggravated in severity from baseline or having their onset between the first dose of the study drug and 30 days after the last treatment dose, death or date of further therapy (whichever comes first). Adverse Events Related to Study Drug or with Unknown relationship occurring more than 30 days after the last dose will also be taken into account as TEAEs.

Summary of overall AEs will be done by System Organ Class (SOC) and Preferred Term (PT), by severity (worst toxicity grade), by relationship to the study drug and by AE outcome. Tables will be

organized by category of events using SOC (i.e. alphabetical order) and PT in descending frequencies (i.e., from higher to lower).

A frequency table or listing will be made for the AEs leading to cycle delay, dose reduction or withdrawal of study medication. Adverse events with outcome of death will also be presented by relationship to the study drugs.

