8.9 Imputation of Incomplete Dates

The dates of certain historical or on-study clinical data are key components for statistical analysis. An incomplete date results from a missing day, month or year; in that case, the missing figure can be imputed, thus allowing the calculation of variables, such as duration and time of a specific event. However, when all dates (day, month and year) are missing, no imputation will be done unless otherwise specified. Whenever imputations are applicable, it will be clearly specified in the corresponding shell table, listing or figure in sections 10-16 of this SAP.

Before Registration

If the day of a month is unknown, then the imputed day will be the 1st. of the month; if the month is also unknown, then the imputed date will be the 1st of July. This assumption will only be valid if the imputed date occurs earlier than the first dose administration date; otherwise the imputed date will be the first day of the month of administration of the first dose (i.e. 01/ month of administration of the first dose/year).

Between treatment start and end of treatment

All date variables during treatment where information is needed and is not fully available, for example adverse events or concomitant medications, will be subject of imputation by means of SAS programming. If the day of a date is unknown then the imputed day will be 1, if the month and/or year is also unknown then the imputed date will 1/January (this assumption will be valid if the imputed date is later than the treatment start date; otherwise, the imputed date will be the treatment start date).

After End of Treatment

To ensure the most conservative approach for the time-to-event variables (i.e., DR, PFS and OS), which can be affected by missing values, the following rules will be implemented: if the day of a date is unknown then the imputed day will be the 1st; if the month is also unknown, then the imputed date will be the 1st of July. This assumption will be valid if the imputed date occurs later than the last drug administration date; otherwise the imputed date will be the date of the last drug administration plus the predefined cycle length (i.e., 21 days if PM01183), except if the patient dies before, in which case the date of death minus 1 will be used. For OS, if a patient dies the imputation event date should be the last date the patient is known to be alive minus one day.

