For the determination of treatment emergent AEs with incomplete dates that do not allow to know if they occurred during the treatment period, the following imputation rules will apply:

- If the start day, month and year are missing, the event will be considered treatment emergent.
- If the start day and month are missing, no date imputation will be performed but the event will be considered TEAE, if the reported year is the same or occurs after the infusion year and also the reported year is the same or occurs before the EOT year.
- If the start day is missing, no imputation date will be performed but the event will be considered TEAE, if the reported month and year occur after the first infusion date (month/year) and before the EOT date (month/year).

-

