Patient id.	Visit	Date	n	Alpha-1-acid glycoprotein (MG/DL)	Comments 1	Comments 2

Listing 14.1.13: Coagulation laboratory values.

Patient id.	Visit	Date	n	Clinically indicated repeat required?	INR (ratio)	PT (sec/ratio)	PTT (sec/ratio)

Listing 14.1.14: Physical examination.

Patient id.	Visit	Not done	Date	Abnormalities	Weight (Kg)	Height (cm)	BSA (m2)	Body System	Findings	Clinical Significance

Listing 14.1.15: Performance status.

Patient id.	Not Done	Visit	ECOG

Listing 14.1.16: Vital signs.

Patient id.	Not done	Visit	Date	Heart Rate (BPM)	Systolic (mmHG)	Diastolic (mmHG)	Temperature (°C)

Listing 14.1.17: Electrocardiogram.

Patient id.	Not done	Visit	ECG Date	Result	Abnormal, specify	PR Interval(msec)	Heart rate (bpm)	QT Interval(msec)	QRS Interval(msec)	Corrected QT Fridericia

Listing 14.1.18: LVEF.

Patient id.	Not done	Visit	LVEF Date	Type	Value	Range	Result	Abnormal, specify	Reason for clinically indicated

Listing 14.1.19: Prophylactic medication.

Patient	Visit	Medication	Drug	...*	Route	Daily	Units	Start	End	Time	Taken per	Specify

id.			Type			Dose		date	date		protocol	
-----	--	--	------	--	--	------	--	------	------	--	----------	--

(*) ATC1, ATC2, ATC3, ATC4.

Listing 14.1.20: Drug administration.

Patient id.	Visit	Admin. date	Start time	End time	Intended dose	Total dose	Adm. Volume	Reductions		Delays		Dose interrupted?
								Dose reduced?	Reason	Dose delayed?	Reason	

Listing 14.1.21: Adverse events (including adverse events at baseline).

Patient id.	Adverse Event Verbatim	NCI-CTC Grade	SAE	Onset cycle	Onset date	Ongoing	End cyc.	End date	Ongoing/Continuing	Relationship Specify	Action taken	Seriousness Criteria

Listing 14.1.22: Concomitant therapy/procedures.

Patient id.	Medication type	Medication	Reason	...*	Route/Dose(Units)/Time interval	Start date	End date	Indication	AE	Other

(*) ATC1, ATC4

Listing 14.1.23: Tumor assessment.

Patient id.	Target			Non target		New lesions		
*	Sum of Diameters	Var.(%)*	Response	...*	Longest diameter	Non-measurable

(*) Visit, Not done, lesion, organ site, date, method. Sort by Visit and then by Start date,

Listing 14.1.24: Evaluation of response by cycle.

Patient id.	Visit	Not done?	Date	Response Target lesions	Response Non Target Lesions	New lesions?	Overall cycle response

Listing 14.1.25: Best study overall response by IA and IRC and End of treatment.

Patient id.	CTFI*	Best Response by IA**	Best Response by IRC*	End of treatment Reason	End of treatment, Specify

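### SAP 8.9: the missing-day rule leaves out AEs in the first-infusion and EOT months, the only ones in doubt, and an imputed death falls before the last date known alive

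*SAP*

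**What the plan says.** The closing rules of SAP 8.9 apply to adverse events with "incomplete dates that do not allow to know if they occurred during the treatment period". There are three:

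- Whole start date missing: the event is treatment-emergent.
- Day and month missing: it is treatment-emergent "if the reported year is the same or occurs after the infusion year" and, likewise inclusively, no later than the EOT year.
- Only the day missing: no date is imputed, and the event is treatment-emergent "if the reported month and year occur after the first infusion date (month/year) and before the EOT date (month/year").

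SAP 7.1 defines a TEAE as an event aggravated from baseline or "having their onset between the first dose of the study drug and 30 days after the last treatment dose", with death or further therapy ending the window earlier. Events related to the drug or with "Unknown relationship occurring more than 30 days after the last dose will also be taken into account as TEAEs". Protocol 5.2.1.1 sets the EOT date at 30 days after the last dose, or at new therapy or death if earlier, so the window ends at EOT.

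For time-to-event variables after end of treatment, SAP 8.9 gives a general rule introduced by "To ensure the most conservative approach for the time-to-event variables (i.e., DR, PFS and OS"): an unknown day becomes the 1st and an unknown month becomes 1 July. It then adds: "For OS, if a patient dies the imputation event date should be the last date the patient is known to be alive minus one day".

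**The concern.** A month strictly between the first-infusion month and the EOT month is on treatment whatever the day, so no rule is needed there. Doubt exists only in the two boundary months, and the third bullet leaves both out. It also reverses the sensible ordering, because a better-dated event is treated worse than one dated only by year or not dated at all.

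At stake are the TEAE summaries (SAP Table 12.2.2.1 and the AE tables that follow it) and the TEAE rows of the cause-of-death table (12.3.2.1). In the first-infusion month the loss can include related events. In the EOT month it falls mainly on unrelated ones, because SAP 7.1 still counts related or unknown-relationship events after the 30-day window.

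The OS sentence has two faults. It dates a death before a day on which the patient was documented alive. It also does not say when it replaces the general rule just above it, which names OS too.

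**Working it through.** The plan gives no figure here to reproduce, so the check applies the rules as written.

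**Example.** First infusion 10 March 2016, last infusion 31 March, EOT 30 April.

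| Recorded start | Test | Result |
|---|---|---|
| March 2016 | March after March? No | Not TEAE |
| April 2016 | April before April? No | Not TEAE |
| 2016 only | Same year at both ends | TEAE |
| Undated | None | TEAE |

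**Share of on-treatment days in a boundary month.** Inputs: 21-day cycles (Protocol 6.3) and EOT = last dose + 30 days (Protocol 5.2.1.1). Assumptions: no delays, no earlier death or new therapy, onset spread evenly, and every first-infusion date in 2016–2017 (731 dates) equally likely.

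Window length after k cycles, counting both ends: W = 21(k − 1) + 31 days.

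Mean number of window days in the first-infusion month: sum of L(L + 1)/2 over the 24 months, divided by 731, where L is the month length. This is 11,505/731 = 15.74 days. Dividing by W gives the first-infusion share. The EOT-month share comes from enumerating the same dates.

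| Cycles | W (days) | First-infusion month | EOT month only | Both | Start dates with no qualifying month |
|---|---|---|---|---|---|
| 1 | 31 | 15.74/31 = 50.8% | 48.9% | 99.6% | 99.6% |
| 2 | 52 | 15.74/52 = 30.3% | 30.3% | 60.5% | 32.6% |
| 4 | 94 | 15.74/94 = 16.7% | 16.7% | 33.5% | 0% |
| 6 | 136 | 15.74/136 = 11.6% | 11.6% | 23.2% | 0% |

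Columns may not add exactly because of rounding. From 3 cycles on, every start date has at least one qualifying month.

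**Sensitivity to delay.** With one week of delay in every cycle (28-day spacing), W = 28(k − 1) + 31, and the two-month share is 53% for 2 cycles, 27% for 4 and 18% for 6.

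**Cycle 1 alone.** The mean number of the 21 days that fall in the first-infusion month is 21 − 210 × 24/731 = 14.1, or 67%.

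**Inclusive comparison.** With same-or-after and same-or-before at month level, 100% of on-treatment days qualify in every scenario. Under the written rule, no boundary-month event qualified for any start date with 1 to 11 cycles.

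**OS.** For a patient last known alive on 15 June 2017, the rule gives death on 14 June. Adding a day gives 16 June. The difference is 2 days: 2/30.44 = 0.07 month, less than one unit of the single decimal reported under SAP 8.10.

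**The case against.** The case for treating this as a small wording slip is reasonable, and several parts of it stand.

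- **Non-TEAE is inferred.** The bullet says when an event counts and has no otherwise clause. Events aggravated from baseline count separately under SAP 7.1.
- **Another rule points the other way.** For dates between treatment start and end of treatment, SAP 8.9 imputes day 1, no earlier than treatment start, and names adverse events. That would place a boundary-month event on treatment. But the TEAE bullets are the specific rule and forbid imputing a date, so this is an unresolved conflict and not a remedy.
- **Other data may settle many cases.** "Listing 14.1.21: Adverse events (including adverse events at baseline") carries an onset-cycle field. Protocol 7.7.1 stops AE collection at 30 days after the last dose or at new therapy, and before treatment only SAE information is required (Protocol 5.4). These facts shrink the uncertain group, but SAP 8.9 does not use them. They also imply that most recorded boundary-month events really are on treatment, so leaving them out is the wrong default.
- **A drug-related event cannot precede the first dose.** True, but the bullet tests dates only.
- **The percentages are not an effect size.** Correct. They are conditional shares of calendar days.
- **Much is unaffected.** ORR, the laboratory toxicity tables and the SAE tables not labelled treatment-emergent (12.3.1.4 and 12.3.1.5) do not rest on this rule.

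These points limit the consequence. None makes the third bullet do what it was written to do.

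**Conclusion.** Both defects are in the current text. The missing-day bullet admits only events that were never in doubt and leaves out all those that were, in the direction of fewer TEAEs. For an unknown-day event not otherwise placed on treatment, the upper bound on the share lost is 99.6%, 61%, 33% and 23% after 1, 2, 4 and 6 cycles. The first-infusion month alone, which the late-event clause of SAP 7.1 cannot recover, accounts for 51%, 30%, 17% and 12%. These figures rest on undelayed cycles, EOT 30 days after the last dose and even onset. The number of such events is not documented, so the effect on the TEAE tables cannot be stated.

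The OS rule yields an impossible date. Its certain effect is negligible and does not favour the drug. A larger shift arises only if the sentence is read as overriding a known month of death. Contact after progression may be as sparse as every six months (Protocol 5.9), so a death could then move by months.

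The text should be corrected before analysis, although the primary endpoint is not affected.

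**What to change.** - **TEAE, day missing:** count the event when its month and year are the same as or later than those of the first infusion, and the same as or earlier than those of EOT. This matches the year-level bullet.
- **Precedence:** add a line saying that the TEAE bullets decide treatment-emergent status, and that the day-1 rule supplies dates for AEs already known to be on treatment.
- **OS:** when the month and year of death are known, apply the section's general rule, but never earlier than the day after the last date known alive. Otherwise use the last date known alive plus one day.

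The cost is two revised sentences, one added line and minor programming. Slightly more TEAEs will be counted, including some events in the first-infusion month that began before dosing. The year-only and undated rules already accept that misclassification.

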8.10 Decimal Places

By default, all numeric results will be rounded to one decimal, except when variables are integers; in that case, they will be reported without decimals (for example, age in years, number of sites, etc.). Three decimal places will be used for Hazard Ratios or Odds Ratios. Four decimal places will be used for p-values.

8.11 Subgroup Analyses

Specific subgroup efficacy analyses will be done for patients with SCLC. These analyses will be performed by IA/IRC and in all evaluable/all treated patient populations, pre-specified analyses are by CTFI defined as the time from the last dose of the last platinum containing therapy to the occurrence of progressive disease,(< 90 days and \geq 90 days and/or Refractory (RR) [$<$ 30 days], Resistant (R)[\geq 30 and $<$ 90 days], Sensitive (S) [\geq 90 and $<$ 180 days] and Very Sensitive (VS)[\geq 180 days]), excluding patients with CTFI $<$ 30 days and considering event to clinical progressions although they

were not documented by radiological images. Any other exploratory analyses requested by the physician at the time of the analysis will be clearly explained, specifying the selected patient population and following the same layout detailed for the other subgroup analyses.

If the number of patients recruited in any cohort differs at least 10% from the sample size assumptions, a sensitivity analysis for main efficacy endpoints using all evaluable patients will be performed.

Pre-specified safety subgroup analyses are: by sex (male vs. female), by age (<65 years-old vs. ≥65 years-old), by race (white vs. other), by number of prior lines (1 vs. >1 line), by BSA (<1.8 vs. ≥1.8) and by geographical area (USA vs. Europe vs. rest of the world).

No differentiation by center is planned.

8.12 Methods for Handling Missing Data

Missing values will be tabulated with their frequency but they will not be included in the calculation of percentages.

8.13 Interim and Group Sequential Analyses

An interim analysis to reject H0 (non-binding) or to reject H1 (futility) in each tumor type is planned after the recruitment of 15 evaluable patients in each cohort. The Gamma family boundary will be used to control the type I error, the parameter to reject H0 is fixed as -1 and the parameter to reject H1 is fixed as 0. If none of the first 15 evaluable patients in a specific cohort has a confirmed response, the alternative hypothesis will be rejected, according to boundaries and sample size assumptions, and recruitment will be stopped. If the number of responding patients is already two or more at the interim analysis, then H0 could be rejected and the study will have enough power to be stopped. On the contrary, if there is one confirmed response, the recruitment will be continued to up to 25 evaluable patients.

In particular, in the SCLC and endometrial carcinoma cohorts, the analysis at 25 evaluable patients will serve as second interim analysis to decide the continuation of recruitment. Two objective responses will be required to expand the accrual up to 100 and 50 evaluable patients respectively.

- For the SCLC cohort, the type I/II error will be controlled with a Gamma family boundary (-1 to reject H0, 0 to reject H1)
- For the endometrial carcinoma cohort, the type I/II error will be controlled with a Gamma family boundary (-1 to reject H0, -3 to reject H1)

8.14 Identification of Fixed or Random Effects Models

Not applicable.

8.15 Data Analysis Conventions

All data analysis conventions, data calculations and grouping needed to perform the statistical analysis not included in this SAP will be described in separate document.

9 STATISTICAL SOFTWARE

Medidata Rave® EDC will be used for data entry and clinical data management.

EAST v5.4 has been used to calculate sample size. SAS v9.2 or higher will be used for all statistical analysis outputs.

APPENDIX I

Statistical output will be displayed by cohort of tumor types and/or total population, and it will be clearly identified with labels (also for subgroup analyses).

Each table, listing and figure will have a comprehensive header identifying the tumor type (cohort) or the total population (if applicable).

For this reason each SAP Table/Listing/Figure will have different granularity, i.e Table 11.1.1.1.x where “x” is a different sublevel of granularity. The following values apply:

Table/Listing/Figure granularity level	Contents
none	Totals all cohort
.b	BRCA 1/2-associated metastatic breast carcinoma
.i	Biliary tract carcinoma
.c	Carcinoma of unknown primary site
.e	Endometrial carcinoma
.w	Ewing’s family of tumors (EFTs)
.g	Germ cell tumor (GCTs)
.h	Head and neck carcinoma (H&N)
.n	Neuroendocrine tumors (NETs)
.s	Small cell lung cancer (SCLC)
.s1	Resistant*
.s2	Sensitive*

(*)For tables to be produced for resistant (.s1) and sensitive (.s2) populations, please see indications in the respective table or figure footnote.

Summary tables will have source data footnotes that will refer to the relevant listings. The tables' layout may change to adequately accommodate cohort size as appropriate.

If the number of categories or items does not yield appropriate tabular or graphic representations, detailed listings will be shown instead.

10 Study Patients

10.1 Patient Disposition

Main characteristics concerning inclusion in the study, withdrawal from the study and protocol deviations will be displayed in this section.

Each table, listing and figure will have a comprehensive header identifying the tumor type (cohort) or the total population (if applicable).

Table 10.1.1 Number of patients included, treated and evaluable for the primary endpoint.

	N	%
Included patients		
Eligible patients*		
Treated patients		
Evaluable patients for efficacy**		
Evaluable patients for efficacy by IRC (SCLC cohort)***		

(*) Patients who were considered eligible according to the registration screening form and were accepted to take part in the trial with the sponsor's agreement in the screening reply form. (**) Includes patients treated with early death/or PD not documented by image (early PD). (***) For sensitivity analysis.

Listing 10.1.2 Patients who do not meet all the inclusion criteria.

Patient id.	Criterion number(s) and description

Listing 10.1.3 Patients who meet any exclusion criteria.

Patient id.	Criterion number(s) and description

Listing 10.1.4 Non-evaluable patients for efficacy analysis.

Patient id.	Reason

Listing 10.1.5 Non-evaluable patients for efficacy analysis by IRC (SCLC cohort).

Patient id.	Reason

Listing 10.1.6 Non-evaluable patients for safety (Non-treated patients).

Patient id.	Reason

Table 10.1.7 Patients accrual by institution.

No. of patients included	Country 1		N	%
		Institution 1		
	...			
	Total			
	...	Institution 1		
		...		

	Total	Total		
		Institution 1		
		...		
	Country 1	Total		
		Institution 1		
		...		
No. of patients treated	...	Total		
		Institution 1		
		...		
	Total	Total		
		Institution 1		
		...		

Table 10.1.8 Study dates.

	Total
Date of first registration	
Date of first dose of the first patient	
Date of last registration	
Date of first dose of the last patient	
Date of last dose	
Date of last follow-up*	

(*) Last follow-up, examination or procedure before clinical cut-off or study closure.

10.2 Reasons for Treatment and Study Discontinuation

Each table, listing and figure displayed in this section will have a comprehensive header identifying the tumor type (cohort) or the total population (if applicable). The reasons for treatment discontinuation will be calculated in the treated patient's population. The rest of tables and listings in this section will be calculated in the included patient's population.

Table 10.2.1 Treatment discontinuation.

Reason	N	%
Progressive disease		
Treatment-related adverse event*		
Non treatment-related adverse event*		
Patient refusal to treatment*		
Death**		
Investigator's decision*		
Other*		
Ongoing at cutoff		
Total		

Note: Also for s1 and s2; (*) Specify (see Listing 10.2.2), (**) Cause of Death (See Table 12.3.2.1).

Listing 10.2.2 Reasons for treatment discontinuation other than progressive disease.

Patient id.	CTFI*	Reason	Last cycle	Comments

(*) Only for SCLC patients (RR, R, S, VS).

Table 10.2.3 Reasons for treatment discontinuation by cycles received.

Reason	Last cycle			
	1	2	...	Total

Progressive disease				
Treatment-related adverse event*				
Non treatment-related adverse event*				
Patient refusal to treatment*				
Death**				
Investigator's decision*				
Other*				
Ongoing at cutoff				
Total				

(*) Specify (see Listing 10.2.2); (**) Cause of Death (See Table 12.3.2.1);

When the reason for discontinuation is a study treatment-related adverse event or study treatment-related death, identify patients and describe them in detail here.

Listing 10.2.4 Treatment discontinuation due to adverse events.

Patient id.	CTFI*	Last cycle	Preferred term code	Adverse event reported (verbatim)	Grade	Relationship	Onset date	Resolved date	Seriousness criteria

(*) Only for SCLC patients (RR, R, S, VS).

Table 10.2.5 Study discontinuation.

Reason	N	%
Never treated*		
Study termination (clinical cut-off)		
Patient's refusal		
Death**		
Lost to follow-up		
Other ***		
Total		

Note: Also for s1 and s2; (*) See Listing 10.2.6; (**) Cause of Death (See Table 12.3.2.1); (***) Specify (see listing 10.2.7).

Listing 10.2.6 Patients included but not treated.

Patient id.	Off-study reason

Listing 10.2.7 Study discontinuation due to other reason.

Patient id.	Specify

